# 6. INVESTIGATIONAL MEDICINAL PRODUCT

Additional information on the manufacturing process and testing of the IMP is provided in the Investigator Brochure.

# 6.1. **Product Description**

The investigational medicinal product (IMP) is a Humacyte human acellular vessel (HAV), which is a tissue-engineered vascular prosthesis for arterial bypass in patients with peripheral arterial disease. It is a sterile, non-pyrogenic acellular tubular vessel composed of human collagen types I and III and other extracellular matrix proteins, including fibronectin and vitronectin. The vessel is 6 mm in diameter and approximately 42 cm in length. The product is supplied on a silicone mandrel immersed in normal physiological saline in a sealed and labeled container.

There is no placebo or comparator control group in this study.

#### 6.2. Manufacturer of the IMP

The HAV is manufactured by:

AlloSource [name] USA

Traceability of the HAV during and after the clinical investigation will be achieved by the assignment of lot numbers. A unique identifying lot number will be assigned to each vessel.

### 6.3. Packaging, Storage, and Labeling

**Packaging**: Each HAV is contained in a sealed, flexible plastic primary container closure system that was developed by Humacyte. The system meets container/closure requirements to maintain sterility as well as product and fluid integrity. The vessel is contained inside the system in a fixed manner, immersed in a sterile, phosphate buffered saline. The total volume of the storage solution is approximately 300 mL.

**Storage**: The product is shipped under controlled conditions to maintain temperature at  $4^{\circ}$ C (range: 2 – 10°C). The product should be stored in a refrigerator that maintains this temperature range. The HAV **MUST NOT** be allowed to freeze.

**Labeling**: The IMP will be labeled according to applicable guidelines and relevant regulatory agency requirements. A tamper proof label affixed to the secondary container will be used to ensure that the product is not compromised prior to use.

# 6.4. Implantation of the Humacyte human acellular vessel (HAV)

The Humacyte HAV is implanted using standard vascular surgical techniques similar to placement of standard peripheral vascular prostheses (see study manual for details).

Tunneling of the HAV must be performed using a sheathed tunneler. During tunneling, the HAV should be handled by pulling on the Dacron cuff (see study manual for details)

After placement, HAV patency and integrity are checked by pressurizing the HAV. Prior to completion of surgery angiography is performed to confirm adequacy of the HAV anastomoses, HAV patency and peripheral runoff. The surgical site is closed using standard techniques.

Implantation of the HAV will be undertaken by qualified vascular surgeons experienced in peripheral arterial bypass surgery.

# 6.5. IMP Accountability Procedures

Documentation of receipt, dispensing, and return of all IMP must be maintained by the Principal Investigator or his/her designee. It is the Principal Investigator's responsibility to ensure that all IMPs are kept in a secure location, with access limited to individuals authorized by the Principal Investigator. The product will be shipped with the IMP Receipt Form. Once signed, the original IMP Form should be returned to Humacyte, and a copy will be maintained in the Principal Investigator's Files. The IMP Accountability Log will be used to account for all IMP received, dispensed, and returned and must be maintained by the site until the conclusion of the study, at which time the original will be retrieved by Humacyte or their authorized designee and a copy kept at the site. Following accountability of the IMP by Humacyte or their authorized designee, all unused IMP will be returned to Humacyte.

# 6.6. Assessment of Patient Compliance with IMP

Not applicable.

# 6.7. **Prior and Concomitant Medications**

Prior medications are defined as all prescription medications or non-prescription aspirin taken within 7 days (whether continuing or not) prior to Day 1. All prior and concomitant medications (including immediately pre-surgery and post-surgery medications) must be listed in the patient's medical record and recorded on the electronic case report form (eCRF). Drugs used during anesthesia should be recorded in the anesthesia records but should not be transcribed into the

eCRF. Patients should be questioned at each study visit concerning any new medications or changes in current medications. **Note: particular attention should be made to identify the use** of antithrombotic or antiplatelet agents (e.g., aspirin, clopidogrel, prasugrel, direct thrombin inhibitors, factor Xa inhibitors, or vitamin K antagonists).

For each medication taken, the following information will be collected:

- Medication generic name / components of combination product
- Dose
- Route of administration
- Frequency of administration
- Date started
- Date stopped
- Indication for use

## 6.8. Essential, Precautionary and Prohibited Medications

#### 6.8.1. Essential Medications

All patients should receive both antibiotic and antithrombotic prophylaxis in conjunction with HAV implantation:

#### Antibiotic prophylaxis:

• All patients must have at least 1 day of antibiotic prophylaxis in accordance with local hospital guidelines. Longer antibiotic prophylaxis is at the discretion of the investigator.

#### Antithrombotic prophylaxis:

- Intraoperative heparin: up to 150 IU/kg unfractionated heparin during surgery.
- Further measures to prevent venous thromboembolism are at the discretion of the investigator and may include low molecular weight heparin (LMWH).
- If antiplatelet therapy was not ongoing at the time of surgery, it should be commenced as soon as possible post operatively. Antiplatelet therapy (usually dual therapy with aspirin 81 to 325 mg and clopidogrel 75 mg daily) should continue long term while the HAV is in place. Choice of an alternative antiplatelet regimen if the patient is unable to tolerate aspirin or clopidogrel is at the discretion of the investigator

Confidential

Humacyte, Inc. Study No. CLN-PRO-V004

#### 6.8.2. Restricted Medications

Vitamin K antagonists, antiplatelet agents other than aspirin and clopidogrel, direct thrombin inhibitors and factor Xa inhibitors (e.g., dabigatran, apixaban and rivaroxaban) should be avoided unless essential for treatment of a medical condition arising postoperatively. In that case, consideration should be given to modification or cessation of antiplatelet therapy. Antiplatelet therapy should be restarted on cessation of these anticoagulant drugs.

# 7. STUDY PROCEDURES / EVALUATIONS

# 7.1. Clinical Evaluations Through Month 12

- Medical History: at screening and Day 1, from patient interview and medical records covering relevant past medical history with particular reference to peripheral arterial disease, prior surgical or percutaneous procedures for PAD, other cardiovascular disease and concurrent medical conditions. Failure of optimum medical therapy for PAD should be documented.
- Smoking history and smoking cessation therapy: at screening and Day 1
- PAD symptoms assessment: at screening and all follow up visits from Day 29 onward through Month 12 using the VascuQol instrument (Morgan MBF et al 2001)
- Review of medications: at all study visits; prescription medication and non-prescription aspirin from Day -7 onward (see Section 6.7). Particular attention should be paid to the identification of over-the-counter (OTC) medications containing aspirin.
- Physical Exam: full exam at screening and Month 12 visit or final study visit for early termination (ET). Focused vascular clinical examination of the operative limb (including any ischemic lesions) and HAV at all post-operative visits; physical exam for lymphadenopathy at Day 5 and Day 29; additional clinical exam as needed to evaluate AEs.
- ABI (supine after 5 minute rest): at screening and all follow up visits from Day 29 onward through Month 12
- 6 minute walk test: at screening and at Months 3 and 12
- Vital signs (temperature, heart rate and sitting blood pressure): at screening and all subsequent study visits through Month 12
- Adverse events: post-operatively on Day 1 and all subsequent study visits; the patient will be asked a general question about his/her health and for any HAV problems since the previous visit.
- Angiography / CT angiography: this is a standard part of the pre-operative assessment of PAD patients. Patients should not be considered for the study unless results of a recent (within the 6 months prior to the screening visit and with no significant clinical deterioration subsequently) study are available.
- Vein mapping: this is a standard part of the pre-operative assessment of PAD patients. Patients should not be considered for the study unless results of a recent (within the 6 months prior to the screening visit) are available and indicate the absence of a suitable conduit for autologous vein bypass grafting.
- CT angiography to assess HAV anatomy at Day 29 and Months 6 and 12
- Intraoperative angiography to assess anastomotic anatomy, patency and runoff

- Clinical duplex ultrasound: clinical assessment at all postoperative visits from Day 29 through Month 12 to assess HAV patency, mid HAV diameter and flow rate. The full length of the HAV should be imaged at each assessment to monitor for aneurysm development.
- High resolution duplex ultrasound intra-operatively and at Months 3, 6 and 12
- Endothelium-dependent, flow-mediated vasodilatation assessed by ultrasound (selected patients only at Day 29 and Month 12)
- Electrocardiogram (ECG; 12-lead): at screening
- Documentation of HAV interventions, surgical procedures and any complications immediately postoperatively through Month 12

# 7.2. Clinical Evaluations in Long Term Follow Up (Post Month 12 to Month 60)

- Focused vascular clinical exam of operative limb
- ABI (supine after 5 minute rest)
- SAEs associated with the HAV
- Events of Special Interest as defined in Section 8.4
- Documentation of HAV interventions
- PAD symptoms assessment: VascuQol instrument (Morgan MBF et al 2001)
- Clinical duplex ultrasound: clinical assessment at all long term follow up visits from Month 18 onward through Month 54 to assess HAV patency, mid HAV diameter and flow rate. The full length of the HAV should be imaged at each assessment to monitor for aneurysm development.
- CT angiography to assess HAV anatomy at Month 60

### 7.3. Laboratory Evaluations

#### 7.3.1. Clinical and Research Laboratory Evaluations and Specimen Collection

The following parameters will be measured at screening and Month 6:

- Hematology: hemoglobin, hematocrit, red blood cells (RBC), WBC with differential, platelet count
- Clinical chemistry: sodium, potassium, calcium, blood urea nitrogen (BUN), creatinine, albumin, total bilirubin, glucose (non-fasting)
- Urine or serum human chorionic gonadotropin (HCG) pregnancy test for WOCBP defined as not sterile or not > 1 year postmenopausal (screening only)
- Coagulation: INR and activated partial thromboplastin time (aPTT)

- HbA1c (Screening only)
- PRA

All laboratory tests (except assay of PRA) will be conducted at certified hospital laboratories. Routine monitoring, maintenance or calibration of laboratory equipment is required per local site procedures. Samples for analysis of PRA will be shipped to Humacyte for analysis at a central laboratory.

Details concerning sample collection and processing can be found in the Study Manual.

# 7.4. Imaging Evaluations

#### 7.4.1. CT angiography

At Day 29 and Months 6, 12, and 60 CT angiography of the Humacyte HAV will be obtained using a multi-detector ( $\geq$  16-slice detector) CT scanner. CT angiography images of the entire HAV will be acquired in a craniocaudal direction with a slice thickness of  $\leq$  1 mm using a bolus-tracking technique to optimize contrast opacification with automated injection of iodinated contrast (iohexol or similar).

Details of the procedure and the method of assessment of the images by a core lab will be given in a separate Imaging Procedures Manual.

#### 7.4.2. Duplex ultrasound

Clinical duplex ultrasound examinations will be performed at Day 29 and Months 3, 6, 9, 12, 18, 24, 30, 36, 42, 48, and 54 and will follow standard bypass graft imaging protocols, including B-mode, power duplex and color duplex ultrasound imaging of the HAV with velocity spectral waveform analysis. The purpose of this clinical duplex ultrasound surveillance is to detect HAV stenosis and aneurysm development.

High-resolution duplex ultrasound imaging will be performed at Day 1 and Months 3, 6 and 12 to investigate the structural, mechanical and functional characteristics of the Humacyte HAV. This protocol will involve standard vascular lab imaging equipment and can be accomplished immediately following the clinical scan. The estimated additional scanning time is 15-20 minutes.

A subset of patients will also undergo endothelium-dependent flow-mediated vasodilation (EDFMV) testing of the HAV at Day 29 and Month 12. HAV diameter, time-averaged blood flow velocity and mean blood flow will be measured at baseline and during reactive hyperemia. The

percent change in HAV diameter during reactive hyperemia represents flow-mediated vasodilation, considered evidence of endothelial function.

Details of the procedure and the method of assessment of the images by a core lab will be given in a separate Imaging Procedures Manual.

### 7.5. Study Schedule

#### 7.5.1. Screening (Day -35 to Day -1)

Potential study participants who are being considered for femoro-popliteal bypass surgery will be informed about the study and invited to participate. After explanation of the potential risks and benefits of the HAV and of the study procedures, written informed consent will be obtained. No study specific procedures may be performed prior to patient consent.

The following assessments will be performed within 35 days prior to surgery (Day 1):

- Informed consent
- Medical history
- Review of medical therapy for PAD (exercise program; antiplatelet therapy; management of diabetes, hypertension and dyslipidemias to current guidelines; smoking history and assistance with smoking cessation)
- PAD symptoms (VascuQol)
- Prior and concomitant medications (all prescription medications plus non-prescription aspirin)
- Full physical examination including number, size and location of ischemic lesions on the intended implant leg
- Evaluation of inclusion/exclusion criteria
- ABI measured with patient supine after 5 minutes rest
- 6 minute walk test
- Vital signs (blood pressure, heart rate, temperature oral, axillary or tympanic)
- Review of recent angiography / CT angiography (within previous 6 months and no significant clinical change since then) to confirm length of stenosis / occlusion of superficial femoral artery, length of required HAV and patency of run-off vessels
- Review of vein mapping to confirm absence of suitable autologous conduit
- ECG (12-lead)

- Laboratory testing
  - Hematology: full blood count and differential
  - Clinical chemistry; sodium, potassium, calcium, BUN, creatinine, albumin, total bilirubin, glucose (non-fasting)
  - Urine or serum HCG pregnancy test for WOCBP
  - Coagulation tests: aPTT and INR
  - HbA1c
  - PRA (sample to be taken for later analysis)

#### 7.5.2. Enrollment – Day 1 (HAV Implantation)

Prior to surgery the following assessments will be performed:

- Medical history (change from screening)
- Medication history (change from screening)
- Physical exam including surgical site (and HAV patency), number, size and location of ischemic lesions on the implant limb, and to evaluate any AEs
- Confirmation of eligibility (all screening results reviewed)
- Vital signs (heart rate, blood pressure, temperature oral, axillary or tympanic)
- Adverse events

Intraoperative Procedures:

- Implantation of HAV and documentation of surgical procedure, any complications (e.g., prolonged oozing at anastomoses), and interventions
- Confirmation of adequacy of anastomoses, patency and run-off by intraoperative angiography
- High-resolution duplex ultrasound of the HAV will be performed to provide a baseline for follow up measurements

#### 7.5.3. Follow-up Visits Day 5 through Month 12

#### Day 5 (or prior to hospital discharge if earlier)

- Review of concomitant medications
- Physical exam including surgical site (and HAV patency); lymphadenopathy; number, size and location of ischemic lesions on the implant leg; and to evaluate any AEs
- Vital signs

- Documentation of any HAV interventions
- Adverse events

#### Day 29 (± 4 days)

- PAD symptoms (VascuQol)
- Review of concomitant medications
- Physical exam including surgical site (and HAV patency); lymphadenopathy; number, size and location of ischemic lesions on the implant leg; and to evaluate any AEs
- Clinical duplex ultrasound of the HAV
- EDFMV testing of the HAV (subset of patients) using high resolution duplex ultrasound
- CT angiography of HAV
- Documentation of interventions
- ABI supine after 5 minutes rest
- Adverse events
- Vital signs

#### Months 3, 6 and 9 (± 14 days)

- PAD symptoms (VascuQol)
- Review of concomitant medications
- Physical exam including surgical site (and HAV patency); number, size and location of ischemic lesions on the implant leg; and to evaluate any AEs
- Vital signs
- ABI supine after 5 min rest
- 6 minute walk test (Month 3 visit only)
- Clinical duplex ultrasound of the HAV
- High resolution duplex ultrasound of the HAV (Months 3 and 6 only)
- CT angiography of HAV (Month 6 only)
- Documentation of interventions
- Adverse events
- Laboratory assessments (clinical chemistry, hematology and coagulation, PRA) all at Month 6 only

#### Month 12 (±14 days) and Early Termination

- PAD symptoms (VascuQol)
- Review of concomitant medications
- ABI supine after 5 min rest
- 6 minute walk test
- Clinical and high resolution duplex ultrasound of the HAV
- EDFMV testing of the HAV (subset of patients) using high resolution duplex ultrasound
- CT angiography of HAV
- Documentation of interventions
- Adverse events
- Full physical exam including surgical site (and HAV patency); number, size and location of ischemic lesions on the implant leg; and to evaluate any AEs
- Vital signs

#### 7.5.4. Long Term Follow Up Post Month 12 through Month 60 (± 30 days)

The status of the patient and HAV will be ascertained every 6 months through 5 years after HAV implantation.

- PAD symptoms (VascuQol)
- ABI supine after 5 min rest
- Documentation of interventions
- SAEs
- Events of Special Interest as defined in Section 8.4
- Physical exam of HAV surgical site and distal limb
- Clinical duplex ultrasound of the HAV (Months 18 through Month 54)
- CTA of operative extremity (Month 60 only)

#### 7.5.5. Early Termination Visit

The patient may withdraw from the study at any time at his/her own discretion. The treating physician may also withdraw the subject for safety reasons. If withdrawal occurs before Month 12, the patient will be asked to complete an early termination visit at which all assessments normally performed at Month 12 will be completed. If withdrawal occurs after Month 12 and prior to

Month 60, the patient will be asked to complete an early termination visit at which all assessments normally conducted during the long term follow up visits will be completed.

The reasons for early termination should be recorded in the eCRF.

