## 2.4.3. CLN-PRO-V002 Study Results (24 M)

Recruitment began in October 2013 and was completed in June 2014 with 20 patients implanted. Thirteen patients completed the 2 year follow up visit. Of the seven patients terminating the study early, three died and four were withdrawn after occlusion of the HAV. None of the deaths were considered related to the investigational device or procedure.

Kaplan-Meier analyses in which deaths were censored revealed primary, primary assisted, and secondary patency probability rates of 79.2%, 79.0%, and 89.5% at Week 26, 63.3%, 63.2%, and 84.2% at Month 12, 63.3%, 63.2%, and 79.0% at Month 18, and 58.1%, 57.9%, and 73.7% at Month 24.

Six patients (30%) required at least 1 graft intervention to maintain or restore HAV patency during the study. Four patients required 1 intervention and 1 patient each required 3 and 4 interventions. Most interventions successfully restored patency. However, in 1 patient the graft patency could not be restored and the HAV was replaced with an alternative bypass graft. Two patients, who had previously undergone successful interventions, developed a recurrent thrombosis which was not treated and the HAV was left occluded. Two patients experienced HAV thrombosis with no or minimal symptoms and refused interventions on the HAV.

Confidential

All 20 patients experienced AEs (a total of 92 events). Thirty-one of these events in 13 patients were considered serious. The most frequent AEs reported included graft thrombosis (35% of patients), anastomotic stenosis (20% of patients), lymphocele (20% of patients), and local swelling (15% of patient). Those serious adverse events (SAEs) reported by at least 2 patients were graft thrombosis (6 patients, 30%) and anastomotic stenosis (2 patients, 10%).

No patient showed an increase in PRA levels. Two patients had a significant (>2-fold) increase from baseline in IgG levels. One of these patients experienced a thrombosis of the HAV between 3 and 6 months after implantation, while the other patient has had no HAV-related AEs and continues to have primary patency. Neither patient has had any evidence of dilatation or structural degeneration of the HAV.

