#### 4.2.2. Secondary Endpoints

#### Safety:

- Change from baseline in PRA
- Change from baseline in hematology, coagulation, and clinical chemistry parameters

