#### 7.5.6. Unscheduled Visits

If necessary to evaluate adverse events or HAV complications, additional visits may be scheduled at the discretion of the investigator. At a minimum, HAV status on clinical examination and Doppler ultrasound and adverse events will be recorded.

If, at any of the scheduled visits, duplex ultrasound surveillance suggests the development of  $a \ge 50\%$  stenosis within the HAV but immediate intervention is not required, closer follow up should be considered. Intervention to manage any such stenosis is at the discretion of the investigator taking into account the degree and rate of progression of the stenosis.

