#### Confidential

1 Oct 2020 Version 4.0

	Screening (Days -35 to -1)	D 1	D 5	D 29 +/- 4 days	M 3 +/- 14 days	M 6 +/- 14 days	M 9 +/- 14 days	M12 /ET  +/- 14 days	M18-M60 /ET  +/- 30 days
Documentation of HAV interventions		Х	Х	Х	Х	Х	Х	Х	Х
PAD symptoms assessment (VascuQol)	Х			Х	Х	Х	Х	Х	Х
ABI – supine after 5 minute rest	Х			Х	Х	Х	Х	Х	Х
6 minute walk test	X				Х			Х	
Patient Survival									Х

Abbreviations: AEs, adverse events; D, day; ECG, electrocardiogram; ET, early termination; HAV, human acellular vessel; M, month; PRA, panel reactive antibody.

NOTE: Visits should be performed using the following time windows: Screening, Day -35 to -1; Day 5 (or prior to hospital discharge, if earlier); Day 29, ± 4 days; Months 3,6,9,12, ± 14 days

- 1 Physical examination includes focused vascular clinical exam of HAV site (incl. patency assessment) and physical exam for lymphadenopathy (at D5 and D29) and to evaluate AEs.
- 2 Patients withdrawn before Month 12 should complete an ET visit that correlates with the procedures at Month 12. Patients withdrawn after Month 12 and prior to Month 60 should complete an ET visit that correlates with procedures post Month 12 through Month 60.
- 3 Intraoperative

4 Duplex ultrasound assessment of endothelium-dependent flow-mediated vasodilatation testing in a subset of patients

- 5 Clinical duplex ultrasound not required on Month 60
- 6 CT angiography only performed on Month 60. This is not required as part of an ET visit
- 7 Collection of SAEs and Events of Special Interest through Month 60

If, at any of the scheduled visits through Month 12, duplex ultrasound surveillance suggests the development of  $a \ge 50\%$  stenosis within the HAV but immediate intervention is not required closer follow up should be considered. Intervention to manage any such stenosis is at the discretion of the investigator taking into account the degree and rate of progression of the stenosis.

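### A patient who leaves before Month 6 has no protocol-required post-implant PRA or safety laboratory value, because the early termination visit copies Month 12, which has no blood sample

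*Protocol*

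**What the plan says.** Protocol 4.2.2 names two secondary safety endpoints that depend on blood samples: "Change from baseline in PRA" and "Change from baseline in hematology, coagulation, and clinical chemistry parameters". The PRA response is also a secondary objective (3.2), and 2.5.1 gives PRA as the means of assessing antibody formation against the HAV.

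On timing, Protocol 7.3.1 states: "The following parameters will be measured at screening and Month 6". The visit list for Months 3, 6 and 9 in 7.5.3 reads: "Laboratory assessments (clinical chemistry, hematology and coagulation, PRA) all at Month 6 only". Appendix 1 marks the laboratory row and the PRA row at screening and Month 6 only, and SAP 5.4 repeats that timing.

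On early exit, Protocol 7.5.5 says of withdrawals before Month 12 that "the patient will be asked to complete an early termination visit at which all assessments normally performed at Month 12 will be completed". Appendix 1, footnote 2, agrees: "Patients withdrawn before Month 12 should complete an ET visit that correlates with the procedures at Month 12". The combined list for Month 12 and early termination in 7.5.3 has imaging, ABI, the walk test, VascuQol, physical examination, vital signs, medications, interventions and adverse events, but no laboratory or PRA item. For unscheduled visits, 7.5.6 asks for less: "At a minimum, HAV status on clinical examination and Doppler ultrasound and adverse events will be recorded".

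On analysis, Protocol 9.2 promises descriptive summaries and change from baseline for laboratory data, including PRA. For PRA, SAP version 2.0 (5.4) commits only to listing the date of sample collection. SAP 7.2 deals with partial dates and has no rule for a missing laboratory or PRA value.

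**The concern.** Change from baseline needs a value after implant, and the schedule offers one chance to obtain it. A patient whose HAV occludes at Month 3 and who then withdraws would be asked for CT angiography, duplex ultrasound, ABI and a walk test, but for no blood. That patient drops out of both endpoints.

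Patients lost this way may not resemble those who stay. Protocol 2.5.1 raises the possibility that an immune response damages the HAV, and early failure is one place where such damage might show. Withdrawal after failure is a documented route: Protocol 2.4.3 reports four V002 patients withdrawn after occlusion, and the derivation of abandonment in SAP 4.4.1 includes withdrawal from the study as a recorded action. With 15 patients, one or two missing pairs make a visible difference, and a report of no PRA response could be read as covering everyone implanted when it covers only those sampled.

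**Working it through.** **Step 1. What the schedule requires.**

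| Visit | Chemistry, hematology, coagulation | PRA |
|---|---|---|
| Screening | yes | yes |
| Day 1 to Month 3 | no | no |
| Month 6 | yes | yes |
| Month 9 | no | no |
| Month 12, and early termination before Month 12 | no | no |
| Unscheduled | not required | not required |
| Months 18 to 60 | no | no |

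Required post-implant samples: 1 for a patient who reaches Month 6, 0 for a patient who leaves before it. A patient who leaves between Months 6 and 12 already has the Month 6 value, so the gap is confined to exits before Month 6.

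**Step 2. How many patients.** The plan states no figure to reproduce. Inputs: 15 recruited (SAP 1.5); V002 secondary patency of 89.5% at Week 26, and 4 of 20 V002 patients withdrawn after occlusion within 24 months (both Protocol 2.4.3). That V002 rates apply here is an assumption.

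- Upper figure, if every patient who loses the HAV by Week 26 also exits: p = 1 − 0.895 = 0.105. Expected number = 15 × 0.105 = 1.6. Chance of at least one = 1 − (1 − 0.105)^15 = 0.81.
- Lower figure, scaling the four withdrawals to six months under an assumed constant hazard: p = 1 − (1 − 4/20)^(6/24) = 0.054. Expected number = 15 × 0.054 = 0.8. Chance of at least one = 1 − (1 − 0.054)^15 = 0.57.

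**Step 3. What one or two missing values do to a zero result.**

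- One missing: 0/14 observed, and 0/15 to 1/15 (0% to 6.7%) in the full set.
- Two missing: 0/13 observed, and 0/15 to 2/15 (0% to 13.3%) in the full set.
- The exact two-sided 95% upper limit for zero events, 1 − 0.025^(1/n), is 21.8% for n = 15, 23.2% for n = 14 and 24.7% for n = 13.

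**Step 4. Who can still benefit from an added sample.** Protocol 2.4.1 reports 35 PAD patients implanted by 20 February 2020 and names two PAD studies. V002 implanted 20 (2.4.3), which leaves 35 − 20 = 15 for this study and matches SAP 1.5. From 20 February to 1 October 2020, the date of protocol version 4.0, is 224 days. The Month 6 window closes at about 183 + 14 = 197 days. The 15 were therefore past the Month 6 window by the date of that version. Protocol 9.5 allows up to 25, so at most 25 − 15 = 10 later patients could gain. If all 10 enrolled, the expected number with a gap would be 10 × 0.054 = 0.5 to 10 × 0.105 = 1.05.

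**The case against.** The strongest objection is timing. Because the 15 known patients appear to have passed Month 6 before protocol version 4.0 was dated, the added sample would recover none of them. This stands, and it narrows the protocol change to later enrollees. It does not remove the case for the change: Protocol 9.5 still allows up to 25 patients, and 2.4.1 describes the study as open for enrollment.

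Second, losing the graft is not leaving the study. Withdrawal is at the patient's discretion or by the physician for safety (7.5.5), and follow-up runs to Month 60. A patient with an occluded HAV who stays gives the Month 6 sample. This stands too, and it makes 1.6 of 15 an upper figure for failure-related exits.

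Third, a reader might infer that the PRA result is biased toward no response. The documents do not support that. The suggestive V002 case concerns IgG: two patients had a rise, and "One of these patients experienced a thrombosis of the HAV between 3 and 6 months after implantation", while the other kept primary patency. Protocol 2.4.3 reports no PRA increase in any V002 patient and does not say that the patient with thrombosis withdrew. In V001 and V003 the three PRA elevations are described alongside failed transplants or other serious illness (2.4.5).

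Finally, the study is descriptive, its results are exploratory (SAP 4) and these endpoints are secondary. Early leavers are still covered by adverse event reporting, physical examination and, where tissue is available, histology. That limits the consequence but supplies no post-implant PRA value.

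**Conclusion.** The gap is real and explicit in the schedule: a patient who leaves before Month 6 has no protocol-required post-implant value for two secondary safety endpoints. A site may draw local blood to evaluate an adverse event, so it would go too far to say that no value of any kind can exist. Nothing requires one, however, and PRA is assayed centrally.

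The size is roughly 0.8 to 1.6 of 15 patients, on the assumption that V002 rates carry over. The lower figure also assumes a constant hazard, and the upper that every patient who loses the HAV by Week 26 exits. The missing values may be related to outcome; the direction of any effect on PRA is plausible but unproven.

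In the SAP, a further PRA gap reaches every patient: version 2.0 plans no summary of PRA values, although Protocol 9.2 promises one. The point merits correction, in proportion to secondary endpoints in a descriptive study.

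**What to change.** - **Protocol.** In 7.3.1, 7.5.3, 7.5.5 and Appendix 1, add PRA, hematology, clinical chemistry and coagulation to the early termination visit for any patient who leaves before the Month 6 sample. The cost is a short amendment and one blood draw at an existing visit, with assays already in use, in very few patients. Sampling time will vary for those patients. Deaths and patients who do not attend remain missing. The change helps only patients enrolled beyond the 15.
- **SAP.** In 5.4, replace the listing of the PRA sample date with the summary and change from baseline that Protocol 9.2 promises. Show any early termination value beside Month 6, labeled with its study day. Report how many implanted patients have no post-implant value and why, and limit any statement of no PRA response to the patients actually sampled. This applies to all 15 and costs one table and one listing.
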